## VIGAB-STAT IIa Protocol

thresholds will be as follows: 1) midazolam  $\geq 0.1$  mg/kg/h, 2) propofol  $\geq 50$  mcg/kg/min, and 3) ketamine  $\geq 1$  mg/kg/hr.

### Targeted temperature management

Post-CA practices are evolving with the emergence of highly impactful clinical trials and clinical practices of temperature modulation may vary. It is expected that a subset of patients will be treated with TTM, with target temperatures ranging from 32-37.5 degrees Celsius. Target temperature selection will be left at the discretion of treatment team. Details of TTM phase of care will be collected, whenever applicable.

### Monitoring for and treatment of seizures

Continuous EEG monitoring will be connected as soon as possible after CA, with a targeted time from ROSC to EEG connection of 6-12 hours post-ROSC. For the phase IIa at the University of Florida, the order set for post-CA care includes a STAT order for EEG to be connected, which prompts the EEG technician to contact the bedside nurse to coordinate hookup. The clinical management of status epilepticus in the post-CA period has been standardized via a treatment algorithm at the University of Florida and UF Health Shands Hospital. Diversions from the algorithm will be at the discretion of the treating neurocritical physician and will be documented in study records.

### Monitoring for markers of secondary brain injury (chemical biomarkers)

We will compare changes on NSE over time between VGB-treated and non-VGB-treated PASE subjects as a potential indirect metric of neuroprotection as higher neuronal injury burden is associated with elevated NSE [73-75], GFAP and NfL[76]. Biomarkers will be measured serially at five timepoints including at 0h, 24h, 48h, 72h, and 4d (96h) post vigabatrin administration.

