### Primary outcome

#### A. Primary feasibility outcome – enrollment and drug delivery

We will primarily be looking at the ability to deliver VGB in PASE subjects; the target will be administering 4,500mg (or dose adjusted in moderate and severe impairment) of VGB enterally within **48 hours of PASE onset** in ≥ 80% of enrolled subjects. Given the lack of well-established alternative treatments in this deadly disease, we anticipate 60-75% enrollment of eligible subjects, and will therefore be tracking the ratio between eligible and enrolled subjects, consent rates, and reasons for decline in study participation.

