### Exploratory outcomes

- A. Exploratory efficacy outcomes

- a. Clinically oriented

We will track the time from VGB load to resolution of PASE, time from VGB load to start of anesthetic wean, total duration of anesthetics for PASE treatment, the overall number of ASDs required for status epilepticus resolution, and the changes in neuron specific enolase (**NSE**), glial fibrillary acidic protein (**GFAP**), neurofilament light chains (**NfL**), tau and ubiquitin C-terminal hydrolase L1 (**UCH-L1**) overtime as a potential indirect metric of neuroprotection since higher neuronal injury burden is associated with elevated NSE, GFAP and NfL levels.

- b. Physician-reported

We will record Epidemiology-based Mortality Score in Status Epilepticus (**EMSE**) during index hospitalization to track disease severity. We will record the following outcomes at discharge, 6 months: modified Rankin Scale (**mRS**), Glasgow Outcome Scale- Extended (**GOS-E**), Glasgow- Pittsburgh Cerebral Performance Categories Scale original (**CPC**) and extended (**CPC-E**) in person visits. In case subjects cannot attend in person visits, a structured questionnaire will be employed for telephone assessments (**t-mRS**, **t-CPC**). Cognitive function will be assessed by Montreal Cognitive Assessment (**MoCA**).

- c. Length-of-stay

We will track total duration of anesthetic infusion for status epilepticus treatment, duration of mechanical ventilation, and ICU length-of-stay.

- d. Patient-reported

We will evaluate self-perceived functional outcomes with the 36-Item Short-Form Health Survey (**SF-36**) according to the Core Outcome Set for Cardiac Arrest (**COSCA**) initiative recommendations on the use of outcome measures of health-related quality of life (**HRQOL**).

B. Exploratory safety outcomes

a. Retinopathy

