## 6. Trial design

Phase IIa: This is a feasibility, single center, open-label pilot, with blinded outcome assessment, of early administration a single 4,500mg (or dose adjusted in moderate and severe impairment) VGB in 12 consecutive PASE subjects.

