## Intervention period

### Drug administration

University of Florida (**UF**) Health Shands Hospital is enrolled in the Vigabatrin Risk Evaluation and Mitigation Strategy (**REMS**) program. The Vigabatrin drug supply for this protocol will be purchased, stored, and dispensed through the Investigational Drug Services Pharmacy satellite of the UF Health Shands Hospital Pharmacy Department. The study drug will be segregated from commercial supply Vigabatrin. Investigational supply would be dispensed upon enrollment, consent, and receipt of a valid order for investigational supply Vigabatrin by a protocol authorized prescriber. Prior to dispensing, the protocol-trained, REMS-trained pharmacist would verify the authorized prescriber, patient REMS enrollment, document the REMS ID numbers and obtain authorization to dispense through the REMS program.

Subjects will receive a **one-time loading dose of 4,500 mg of VGB** (or dose adjusted in moderate and severe impairment) in powder for oral solution formulation (9 packets of 500mg each, each mixed with 10 ml of water at room temperature, for a total of 90 ml of water and 4,500mg VGB dosing) will be administered via enteric tube (naso/orogastric or post-pyloric) within **48 hours of status epilepticus onset**. For subjects requiring a dose adjustment for renal impairment, the total volume administered will be dictated by dose of Vigabatrin (10mL of water for each 500mg packet).. If subjects are receiving the study drug through an NG/OG tube that is ordered to be connected to suction, the tube will remain clamped for a minimum of 30 minutes. Vigabatrin will not be co-administered with other enteral drugs, and no drugs will be given +/- 15 minutes of Vigabatrin administration (when possible per standard of care). Subjects will be considered screen failure if VGB is not administered within exact 48 hours from electrographic status epilepticus onset. This dose is in conjunction with a loading dose of ASD according to local practices and standard of care. This will be done within 48h of PASE onset in successfully resuscitated CA subjects.

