## VIGAB-STAT IIa Protocol

a Time in days (D) refers to time from CA, while time in hours (h) refers to time from VGB load, unless otherwise specified.

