## 12. Statistical plan and data analyses

### Phase IIa sample size

12 subjects from the University of Florida

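### The planned NSE comparison needs a vigabatrin-untreated group that the trial does not enroll and the plan does not define

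*Combined protocol and SAP*

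**What the plan says.** The biomarker paragraph of section 6 (Monitoring for markers of secondary brain injury) commits to a between-group analysis: "We will compare changes on NSE over time between VGB-treated and non-VGB-treated PASE subjects". It offers the result as an indirect sign of neuroprotection and sets the sampling times at "0h, 24h, 48h, 72h, and 4d (96h) post vigabatrin administration".

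Other parts of the plan bear on this:

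- **Design (section 6).** The pilot gives "VGB in 12 consecutive PASE subjects".
- **Sample size (section 12).** The entry is "12 subjects from the University of Florida", with no division into groups.
- **Drug administration (section 6).** Every subject is to receive the load. For those who do not receive it in time, the rule is "Subjects will be considered screen failure if VGB is not administered within exact 48 hours from electrographic status epilepticus onset".
- **Exploratory outcomes (section 4).** Change in NSE, GFAP, NfL, tau and UCH-L1 is tracked over time, with no comparator, "as a potential indirect metric of neuroprotection since higher neuronal injury burden is associated with elevated NSE, GFAP and NfL levels".
- **Section 12, Primary outcome and Secondary outcome.** Feasibility rates, pharmacokinetic parameters and summaries of clinical outcomes are listed. No biomarker appears.
- **Section 12, Analysis methods.** The study is not meant to detect treatment effects, and power calculations are left out for that reason.

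**The concern.** A comparison of treated with untreated subjects needs an untreated group, a time origin that both groups share, and a method. The plan supplies none of these. It also points the statistician in three directions: a between-group contrast in section 6, an uncontrolled change over time in section 4, and no biomarker analysis in section 12.

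The risk lies in what fills the gap. An untreated group chosen after the data are in hand could differ from the 12 treated subjects in prognosis, survival and sampling time. A difference in NSE could then be read as neuroprotection and carried into the design of the next phase. The section 4 wording allows a similar misreading without any control group, because it attaches the neuroprotection interpretation to an uncontrolled change.

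**Working it through.** **The plan's own figure.** The only relevant figure is N = 12. It has no derivation and power calculations are deliberately omitted, so there is nothing to reproduce. The check is a count of subjects and an alignment of time scales.

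**1. Untreated subjects by design.** Planned subjects = 12; planned to receive VGB = 12; untreated = 12 − 12 = 0.

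**2. Untreated subjects if delivery fails in some.** The primary feasibility target is dosing within 48 h "in ≥ 80% of enrolled subjects". Assume that the 12 are the enrolled subjects and that those not dosed in time are retained.
- Minimum dosed to meet the target: 0.80 × 12 = 9.6, rounded up to 10.
- Maximum not dosed in the window: 12 − 10 = 2.

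Section 6 classes such subjects as screen failures, and nothing designates them as controls.

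**3. Possible sources outside the 12.** Each was checked for a designation as comparator.

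| Place | What it provides | Named as comparator? |
|---|---|---|
| Section 6, Screening | Log of eligible subjects, to inform later entry criteria | No |
| Section 6, Prognostication, NSE | Routine daily NSE for 5 days | No |
| Section 7, Co-enrollment | Joint enrollment with an observational study | No |
| Section 10, Quality control | One generic mention of a randomization protocol; no arms, ratio or method | No |

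**4. Time zero.** The footnote to the section 8 schedule reads: "Time in days (D) refers to time from CA, while time in hours (h) refers to time from VGB load". The biomarker times are in hours, so they start at the VGB load. Dosing may occur 0 to 48 h after onset of status epilepticus.

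Time since onset = nominal hour + dosing delay.
- 24 h sample: 24 + 0 to 24 + 48 = 24 to 72 h after onset.
- 96 h sample: 96 + 0 to 96 + 48 = 96 to 144 h after onset.
- Maximum offset relative to the sampling span: 48 / 96 = 0.50.

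The ratio shows how far the clocks can drift apart; it is not an estimate of bias.

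**5. Precision, for illustration.** Assume a two-sided 5% level and 80% power, neither of which the plan states. The detectable standardized difference, by normal approximation, is (1.96 + 0.84) × √(1/n₁ + 1/n₂).
- 10 versus 2: 2.80 × √(0.100 + 0.500) = 2.17 SD.
- 12 versus a hypothetical external 12: 2.80 × √(0.083 + 0.083) = 1.14 SD. The approximation is slightly optimistic at this size: with the t distribution, power is 0.802 at 1.2 SD.

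Even with a comparator of equal size, only a very large difference would be detectable.

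**The case against.** The strongest reply is that the sentence speaks of subjects with post-anoxic status epilepticus, not of enrolled subjects, so an outside group may be intended. The primary outcome text expects 60 to 75% of eligible subjects to enroll. Twelve enrolled then imply 12/0.75 = 16 to 12/0.60 = 20 eligible, or 4 to 8 not enrolled. These patients would be in the screening log and might have routine NSE. Cardiac arrest, from which the schedule counts days, is a time origin that untreated patients do have. On this view the comparator is undefined rather than impossible, and aligning the clocks is a matter of re-indexing.

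That much stands: an external comparison could be built. But the plan does not say that non-enrolled patients serve as controls or that consent covers their data, and it specifies no re-indexing.

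A second reply is that the sentence may be carried over from a later phase. The plan marks deferred work explicitly elsewhere (section 4, Specific aims; section 12, Subgroup analysis). This sentence has no such marker, and the next one gives this trial's sampling times.

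A third is that little depends on it: the outcome is exploratory, the plan disclaims efficacy, and missing data and mode of death are already to be recorded. This is fair and limits the weight of the point. It does not remove the contradiction.

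The section 8 schedule is incomplete in the text reviewed, and its biomarker rows are not visible. They are unlikely to define a control cohort, but the statement that none is defined applies to the text available.

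**Conclusion.** The concern holds: the NSE comparison is wrong as written. By design there are 0 untreated subjects against 12 treated. The bound of 2 of 12 applies only if the 12 are the enrolled subjects, the delivery target is met and undosed subjects are retained. The 24 to 72 h and 96 to 144 h ranges assume that the full 48 h dosing window may be used. An external comparator is possible in principle, but none is specified.

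The point should be corrected. It is confined to an exploratory outcome and leaves the primary feasibility and pharmacokinetic outcomes intact.

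**What to change.** 1. **Section 6, biomarker paragraph:** delete the treated-versus-untreated comparison and its neuroprotection interpretation.
2. **Section 4, Exploratory outcomes:** keep biomarker change over time, call it descriptive, and remove the neuroprotection interpretation there too.
3. **Section 12:** for NSE and the other four markers, add the median and IQR at each time, and the within-subject change from the 0 h sample at 24, 48, 72 and 96 h. Plot individual profiles by hours since return of spontaneous circulation. Report how many subjects are still sampled at each time and why samples are missing, because death or withdrawal of life support makes the later samples selective.
4. **If an external comparator is wanted:** limit it to NSE. Before data review, state its source, its eligibility criteria and a time zero that untreated patients also have, such as return of spontaneous circulation or onset of status epilepticus. Label the result hypothesis-generating.

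Steps 1 to 3 cost a few sentences in sections 4, 6 and 12 and no new samples. The trial gives up a between-group claim that its design does not support.

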### Shivering

Shivering will be assessed according to the Bedside Shivering Assessment Scale (**BSAS**). Goals of treatment are to maintain BSAS score 0-1, which will be done for all subjects and tiered prevention and therapeutic approach will be implemented according to institutional practices.

### Screening

Screening will be done according to the inclusion and exclusion criteria and will be performed in multiple clinical areas, including the Emergency Department and ICU. The PI and co-investigators will be responsible for screening the EEG of eligible subjects for PASE development four times daily.

We will maintain a screening log to keep track of all eligible subjects, which will inform future decisions on inclusion/exclusion criteria in the subsequent study phases.

### Blinding

The phase IIa feasibility study is open label. However, EEG recordings and Visual Field Perimetry will be centrally analyzed at the EEG and Visual Screening cores by an assessor that is blinded to the timing of VGB administration and drug levels. De-identified EEG recordings will be exported to Yale University for central analyses by [name], and de-identified Visual Field Perimetry studies will be exported to [name] at Tomas Jefferson University for central analyses in a blinded fashion. Clinical outcomes will be obtained by trained study personnel blinded to the timing of VGB administration and drug levels.

## Intervention period

### Drug administration

University of Florida (**UF**) Health Shands Hospital is enrolled in the Vigabatrin Risk Evaluation and Mitigation Strategy (**REMS**) program. The Vigabatrin drug supply for this protocol will be purchased, stored, and dispensed through the Investigational Drug Services Pharmacy satellite of the UF Health Shands Hospital Pharmacy Department. The study drug will be segregated from commercial supply Vigabatrin. Investigational supply would be dispensed upon enrollment, consent, and receipt of a valid order for investigational supply Vigabatrin by a protocol authorized prescriber. Prior to dispensing, the protocol-trained, REMS-trained pharmacist would verify the authorized prescriber, patient REMS enrollment, document the REMS ID numbers and obtain authorization to dispense through the REMS program.

Subjects will receive a **one-time loading dose of 4,500 mg of VGB** (or dose adjusted in moderate and severe impairment) in powder for oral solution formulation (9 packets of 500mg each, each mixed with 10 ml of water at room temperature, for a total of 90 ml of water and 4,500mg VGB dosing) will be administered via enteric tube (naso/orogastric or post-pyloric) within **48 hours of status epilepticus onset**. For subjects requiring a dose adjustment for renal impairment, the total volume administered will be dictated by dose of Vigabatrin (10mL of water for each 500mg packet).. If subjects are receiving the study drug through an NG/OG tube that is ordered to be connected to suction, the tube will remain clamped for a minimum of 30 minutes. Vigabatrin will not be co-administered with other enteral drugs, and no drugs will be given +/- 15 minutes of Vigabatrin administration (when possible per standard of care). Subjects will be considered screen failure if VGB is not administered within exact 48 hours from electrographic status epilepticus onset. This dose is in conjunction with a loading dose of ASD according to local practices and standard of care. This will be done within 48h of PASE onset in successfully resuscitated CA subjects.

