#### C. Primary pharmacologic outcome: PK – absorption

By analyzing serial VGB levels including baseline, we will validate the drug assay and characterize drug absorption; the target will be achieving a detectable VGB level in the serum of ≥ 80% of

enrolled subjects by 3 hours post-load. We anticipate detectable levels in all subjects by 12 hours. We expect peak concentrations to be delayed by one to three hours in older individuals receiving continuous enteral tube feedings.

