### Secondary outcomes

- A. Secondary feasibility outcome – PASE detection and ultra-early drug delivery
  - a. We will track the proportion of subjects in whom PASE was present upon connection to EEG (onset misses) to explore alternatives to allow prompt EEG monitoring following ROSC.
  - b. We will also track the proportion of enrolled subjects who received a VGB load within 12 and 24 hours of PASE onset to explore the possibility of ultra-early administration of VGB in subsequent phases, as the internalization of GABAA receptors (a key mechanism of treatment refractoriness) is time-dependent[65].

- B. Secondary pharmacologic outcome: PK – elimination

By analyzing serial VGB levels, we will characterize drug elimination. We anticipate undetectable VGB levels in all subjects by 7 days regardless of their renal function. Subjects with normal renal function will have undetectable VGB levels by 72 hours, and those with creatinine clearance less than 30 mL/min will have detectable VGB levels at 72 hours.

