## 5. Eligibility

### Inclusion criteria

After Institutional Review Board approval, individuals (and their legally authorized representative) meeting the following inclusion criteria will be approached: 1) 18 – 80 years of age, 2) non-traumatic CA (regardless of non-perfusing rhythm, etiology, or location of arrest) in whom the decision to treat unequivocal electrographic SE (as defined by the American Clinical Neurophysiology Society[69]: having generalized spike/sharp-wave discharges  $\geq 3\text{Hz}$  or any evolving pattern reaching  $> 4\text{Hz}$ , lasting  $\geq 10$  minutes, or comprising  $> 50\%$  of any hour of recording) has been made. The inclusion criteria will be expanded to include presumed electroclinical status epilepticus defined in this study as ictal -interictal continuum patterns of at least 1Hz as long as patient is treated with an antiseizure medication per the decision of the clinical treatment team. The time of onset for PASE in this setting will be the time of the loading dose of antiseizure medication. 3) requiring anesthetic infusion for any reason, 4) have reliable arterial access for frequent blood sampling and 5) established enteral access within 48h of PASE onset. The patient's legal authorized representative (LAR) will be identified with the clinical, research, and social work teams. The legal authorized representative will be approached to provide consent for participation in the study, during the patient's acute phase of ICU care after cardiac arrest, while the patient is in coma, undergoing continuous seizure monitoring. In the event COVID related restrictions do not allow for the LAR to come to the floor, we will proceed with remote consenting procedures with IRB approved scripts. Should the patient regain consciousness at any time during the 6-month study duration, they will individually be approached to provide their consent for continued participation in the research protocol. Further details on consent process are provided in Section 9.

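### Subjects who miss the 48-hour dosing window are relabelled screen failures, which on the ordinary meaning removes them from the denominator of primary outcome A

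*Combined protocol and SAP*

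**What the plan says.** Primary outcome A (section 4) is the share of subjects given the VGB load enterally within 48 h of onset of post-anoxic status epilepticus (PASE). The target is delivery "in ≥ 80% of enrolled subjects".

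The Drug administration text (section 6, Intervention period) adds a classification rule: "Subjects will be considered screen failure if VGB is not administered within exact 48 hours from electrographic status epilepticus onset". The same text places enrolment before dosing: "Investigational supply would be dispensed upon enrollment, consent, and receipt of a valid order". A subject can therefore be enrolled first and miss the window afterwards.

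Other places bear on the reading:

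- The Inclusion criteria (section 5) set a second onset clock for presumed electroclinical cases: "The time of onset for PASE in this setting will be the time of the loading dose of antiseizure medication". The screen-failure rule refers only to electrographic onset.
- Two other outcomes use the same denominator word. The absorption target (primary outcome C) is a detectable level in at least 80% of "enrolled subjects by 3 hours post-load". The secondary outcome on early delivery reads: "We will also track the proportion of enrolled subjects who received a VGB load within 12 and 24 hours of PASE onset".
- The sample size is given as "VGB in 12 consecutive PASE subjects" in section 6 and as "12 subjects from the University of Florida" in section 12.
- The Trial overview lists enrolment and reasons for screen failure as separate items, and the Screening section keeps a log of eligible subjects.
- Section 12 promises descriptive rates and proportions and a report of missing data. It names no analysis set, denominator or replacement rule.

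**The concern.** A delivery rate measures feasibility only if failed deliveries stay in its denominator. Here the failure event is also the criterion for being called a screen failure, and a screen failure is ordinarily not an enrolled subject. On that reading late delivery cannot lower the rate.

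Misses are realistic. The note on the inclusion window itself calls 48 h very short, given surrogate consent and the need for enteral access.

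The main aim is to prove that delivery in this window is feasible, and the 80% figure is its stated target. A team planning the next phase would see a rate from which late and undosed subjects had been taken out. A delivery failure recorded as a screen failure could also lower the eligible-to-enrolled ratio that outcome A tracks, and so look like a recruitment problem.

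**Working it through.** **Inputs.** From the protocol: the 80% target (primary outcome A) and 12 subjects (sections 6 and 12). The protocol gives no expected on-time rate and omits power calculations, so there is no planned figure to reproduce. The on-time rates p = 0.6 to 0.9 and the splits below are assumptions for illustration.

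**1. What the rule does to the proportion.** Let N be the otherwise eligible enrolled subjects and x those dosed on time.

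- Misses kept: x/N.
- Misses relabelled and removed: x/x = 100% for any x above 0.

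Two kinds of miss could still register: an incomplete dose, and a subject on the second onset clock, because the rule counts only from electrographic onset.

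**2. Example: N = 12, 3 missed.** The exact (Clopper–Pearson) 95% limits are the 0.025 quantile of Beta(x, n−x+1) and the 0.975 quantile of Beta(x+1, n−x).

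- Misses removed: 9/9 = 100% (66.4–100%), target met.
- Misses kept: 9/12 = 75.0% (42.8–94.5%), target not met.

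**3. Chance of meeting the target when misses are kept.**

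- If 12 means enrolled: 0.8 × 12 = 9.6, so at least 10 must be on time (10/12 = 83.3%). The chance is P(X ≥ 10) with X ~ Bin(12, p).
- If 12 means dosed on time: 12/N ≥ 0.8 requires N ≤ 15, so at most 3 misses are allowed. The chance is the negative binomial P(at most 3 misses before the 12th dosed), which equals P(X ≥ 12) with X ~ Bin(15, p).

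| Assumed on-time rate | 12 enrolled, misses kept | 12 dosed, misses kept | Misses removed (timing part) |
|---|---|---|---|
| 60% | 8.3% | 9.1% | met |
| 70% | 25.3% | 29.7% | met |
| 80% | 55.8% | 64.8% | met |
| 90% | 88.9% | 94.4% | met |

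**4. Other outcomes using the same word.**

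- Delivery by 24 h, if 6 of the 9 were dosed by then: 6/9 = 66.7% (29.9–92.5%) with misses removed, 6/12 = 50.0% (21.1–78.9%) with misses kept.
- Detectable level at 3 h, if 8 of the 9 dosed are detectable: 8/9 = 88.9% (51.8–99.7%) meets 80%; 8/12 = 66.7% (34.9–90.1%) does not. This shows only that the denominator must be named. A subject who was never dosed has no 3 h post-load sample, so the dosed set is the natural choice here.

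**The case against.** The strongest reply is that no sentence removes screen failures from outcome A. A target below 100% makes sense only if enrolled subjects can miss, enrolment precedes dispensing, and the design calls for consecutive subjects. One can therefore read *enrolled* as fixed at consent, with *screen failure* used loosely. That reading is possible, but it sets aside the ordinary meaning of the label, and nothing in the protocol supports it over the other. The same data would then give 75% or 100% depending on the reader.

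Several further points stand in part:

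- The screening log and screen-failure reasons may let a reader rebuild the count. That lessens the harm but does not change the 80% figure.
- The analysis is descriptive with no decision rule. But proportions are the whole feasibility analysis, so the denominator determines the result.
- The on-time rates and splits are invented. They show the mechanism and do not forecast how many subjects would be relabelled.
- The absorption example is not evidence of harm, since the dosed set is the sensible denominator there.
- Eligibility requires enteral access within 48 h of onset. Subjects without it stay outside the rate even after the fix below, so the rate remains conditional on access.

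**Conclusion.** The concern holds. Followed as written and on the ordinary meaning of screen failure, the rule makes the timing part of primary outcome A close to automatic. In the 12-subject example it turns 75.0%, below target, into 100%. With misses kept, the chance of reaching the target at a true on-time rate of 60% is about 8–9%; with misses removed, the timing part is met whatever the rate.

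The conclusion rests on the ordinary meaning of the label and on the absence of any definition of *enrolled*. The sizes rest on the assumed rates and splits. The defect lies in the definition of the first primary outcome, so it should be corrected before the result is reported.

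**What to change.** 1. Define *enrolled* as consented, with confirmed PASE, and meeting all other inclusion and exclusion criteria in section 5, leaving the enteral-access criterion as it is. Consented subjects who never develop PASE or who fail another criterion remain screen failures.
2. In Drug administration, replace the screen-failure label for enrolled subjects with a statement that a subject not dosed in the window counts as a delivery failure in primary outcome A. This changes the classification only, not whether or when anyone is dosed.
3. Reconcile the onset definitions in Inclusion criteria and Drug administration so that one defined time zero applies to each subject.
4. State whether the 12 are enrolled or dosed subjects.
5. Report n/N with an exact 95% CI, and give the target as a count (at least 10/12 if 12 are enrolled).
6. Use all enrolled subjects for the 12 h and 24 h delivery rates, and the dosed set for the pharmacokinetic outcomes.

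**Cost.** Edits to sections 4, 5, 6 and 12, with no new procedures. The reported delivery rate may be less favourable. If 12 means enrolled, fewer subjects may give pharmacokinetic data: 12p = 7.2, 8.4 and 9.6 expected dosed at assumed rates of 60%, 70% and 80%. If 12 means dosed, more must be enrolled: 12/p = 20.0, 17.1 and 15.0 expected at the same rates.
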